## 2.0 CLINICAL TRIAL SYNOPSIS

Study Title	An Open Label, Phase 2 Pharmacokinetic Study of Pre-Surgical Intramuscular and Intraductal Fulvestrant in Women with Invasive Breast Cancer or DCIS Undergoing Mastectomy or Lumpectomy
Study Number	ATOS-2015-007
Objectives	
To study the safety and tolerability of intraductal administration of fulvestrant (Faslodex®, ICI 182,780) in women with Stage 1 or 2 invasive ductal carcinoma (or mixed ductal and lobular) or DCIS, prior to mastectomy or lumpectomy.
 
To determine the pathological effects, specifically changes in Ki67, ER/PgR expression between the pre-fulvestrant biopsy and the post-fulvestrant surgical specimen.
 
To compare an abbreviated (Pharmacokinetic-PK) profile of standard intramuscularly administered (500 mg) with the intraductal instillation of single-dose (500 mg maximum) fulvestrant. To determine and compare breast tissue fulvestrant distribution.

Study Drug	Fulvestrant (Faslodex ® )
Study Design	This is a single-dose observational and comparative study
No. of Subjects	30 evaluable subjects with breast cancer and scheduled for mastectomy or lumpectomy.
Routes of Administration	Intramuscularly (n = 6) and intraductally (n = 24)
Dosage (Single dose)	
Intramuscularly: 500 mg – to establish reference proliferation markers (Ki67) responses and PK-values.
 
Intraductally: up to 500mg

Delivery Device	
Intramuscularly: Fulvestrant is supplied, from the manufacturer, as two, 5-mL prefilled syringes, containing 50 mg/mL (250 mg/syringe)
 
Intraductally: Jabczenski Ductogram Cannula® Microcatheter or IntrocanSafety® IV Catheter and the FullCYTE® Breast Aspirator. Detailed instructions for intraductal fulvestrant administration are located in the administration manual provided

Inclusion Criteria	
 
1. Female
 
2. 18 years of age or older
 
3. Scheduled to undergo mastectomy or lumpectomy for Invasive Breast Cancer (clinical stage 1 or 2, ER+ low- to medium grade) or DCIS
 
4. Pathological diagnosis of Invasive Ductal Carcinoma or Ductal Carcinoma in Situ (DCIS) requiring mastectomy or lumpectomy. Mixed ductal and lobular tumors are permitted).
 
5. Estrogen Receptor positive biopsy, as determined from a biopsy specimen obtained no more than 3 months prior to entry
 
6. ECOG performance scale of 0-1 (Appendix A)
 
7. Adequate organ function as defined by the following criteria: 
 
a. Absolute neutrophil count (ANC) <math>\geq</math> 1500/<math>\mu</math>L
 
b. Platelets <math>\geq</math> 100,000/<math>\mu</math>L
 
c. Hemoglobin <math>\geq</math> 9.0 g/dL
 
d. Creatinine <math>\leq</math> 2 times upper limit of normal
 
e. Bilirubin <math>\leq</math> 2 times upper limit of normal
 
f. Transaminases (AST/SGOT and ALT/SGPT) <math>\leq</math> 2.5 times upper limit of normal
 
 
 
8. Able to sign informed consent
 
9. Willing to use effective contraception for at least 100-days post study drug administration if subject is pre-menopausal.
 

**ATOS-2015-007: An Open Label, Phase 2 Pharmacokinetic Study of Pre-Surgical Intramuscular and Intraductal Fulvestrant in Women with Invasive Breast Cancer or DCIS Undergoing Mastectomy or Lumpectomy**

Exclusion Criteria	
 
1. Concurrent treatment with another anti-estrogen
 
2. Presence of an active infection requiring systemic therapy.
 
3. The following conditions contra-indicating fulvestrant administration:             
 
a. Subjects with bleeding diatheses, thrombocytopenia or current anticoagulant use (excludes aspirin or anti-inflammatory agents)
 
b. Subjects with a known hypersensitivity to fulvestrant or any of its formulation components including castor oil, alcohol, benzyl alcohol, and benzyl benzoate.
 
c. Severe hepatic impairment.
 
 
 
4. Prior surgery on the ipsilateral breast which interrupts communication of the ductal systems with the nipple
 
5. Prior radiation to the breast
 
6. Pregnant or lactating
 
7. Impaired cardiac function or history of cardiac problems of NYHA Class 111 and IV
 
8. Poor nutritional state as indicated by a BMI of below 20
 
9. Presence of serious infection not controlled with systemic therapy
 
10. History of allergies to Lidocaine or Novocain
 
11. Concurrent participation in an experimental drug study
 

Study Duration	Total 12 – 36 months, active phase 6 weeks followed by inactive phase (enrollment dependent)
No. of Trial Sites	One.
Study Rationale	This study is being conducted to develop the preliminary safety and feasibility of this route of administration to provide information necessary to develop future clinical studies.

### 3.0 LIST OF ABBREVIATIONS & DEFINITION OF TERMS

ADH	Atypical ductal hyperplasia
AE	Adverse Event
AI	Aromatase inhibitor
AIC	Akaike Information Criterion
Alb	Albumin
ALT	Alanine aminotransferase
ANC	Absolute neutrophil count
AST	Aspartate aminotransferase
ATOS	Atossa Genetics, Inc.
AUC	Area under curve
BSA	Body Surface Area
BUN	Blood urea nitrogen
CFR	The United States Code of Federal Regulations
Cr	Creatinine
CRA	Clinical research associate
CRF	Case report form
CTCAE	Common Terminology Criteria for Adverse Events
CTMF	Clinical Trial Master File
DMP	Data Management Plan
DCIS	Ductal Carcinoma In Situ
DLT	Dose limiting toxicities
ER	Estrogen receptor
FDA	United States Food and Drug Administration
GCP	Good Clinical Practice
Glu	Glucose
HE	Hematoxylin and eosin
HPLC	high performance liquid chromatography
H & P	History & Physical
ICH	International Conference on Harmonization
ID	identification
IM	Intramuscular
IRB/IEC	Institutional Review Board/Institutional Ethics Committee
K	potassium
mg	milligrams
mL	milliliter
MRI	Magnetic resonance imaging
Na	Sodium
NAF	Nipple aspirate fluid
NCI	National Cancer Institute (United States)
NYHA	New York Heart Association
PgR	Progesterone Receptor
PK	Pharmacokinetics
PLD	Pegylated liposomal doxorubicin, trade name Doxil®
SGOT	Serum glutamic oxaloacetic transaminase
SGPT	Serum glutamic pyruvic transaminase
SAE	Serious adverse event
SERM	Selective estrogen receptor modulator
Tbili	Total bilirubin

#### 4.0 BACKGROUND INFORMATION

Breast cancer is the leading cause of cancer in women in the United States and the second leading cause of cancer related death. An estimated 215,000 American women will be diagnosed with breast cancer in 2015 and over 39,000 women will die due to their disease. Approximately 1 in 8 women in the United States will be diagnosed with breast cancer in their lifetime. Because of the increased incidence in breast cancer, both *in situ* and invasive, much research has been done to identify those women at risk for the disease and ways to prevent it from occurring. Only two Selective Estrogen Receptor Modulators (SERMs), tamoxifen and raloxifene, are currently approved in the USA for the prevention of breast cancer in high-risk women. The aromatase inhibitors exemestane and anastrozole have been evaluated successfully in randomized trials, but have not been approved in the US specifically for a prevention indication.

Based upon demographics and registries, data reflect that women whose first-degree relatives (e.g., mother, sister or daughter) have had breast cancer are 3 to 4 times more likely to develop breast cancer than those without family history. A woman's reproductive history, menopausal status, prior breast surgeries or breast abnormalities also increases her risk of developing breast cancer. Currently, several different statistical models, such as the Gail, IBIS and Claus models, exist which attempt to predict the 5-year, 10-year and lifetime risk of women to develop breast cancer. The models are based upon the subject's reproductive history as well as family history related to cancer, specifically breast cancer. These models have been useful in identifying subjects at increased risk for developing breast cancer, and selection for genetic counseling or more intensive diagnostic surveillance, but do not appear to have spurred the development of new chemo-preventive strategies. The mission of this study's Sponsor, Atossa Genetics Inc. (ATOS), is to reduce the risk for breast cancer and reduce the morbidity associated with breast cancer by developing a local, minimally invasive therapy with fewer side effects than typically seen with systemic therapy.

The currently available options for prevention are oophorectomy (surgical removal of the ovaries), bilateral mastectomy, or pharmaceutical therapy, such as tamoxifen or anastrozole. None of these options for prevention are without side effects or consequences.

Oophorectomy is associated with the side effects associated with early menopause. Surgical removal of the breast tissue, although successful in reducing the likelihood of developing breast cancer by 97% is a lengthy and morbid surgery, not without complications. With long-term systemic use, tamoxifen puts women at risk for thromboembolism, cataracts, uterine cancer, and vasomotor events. Much research is being conducted looking at aromatase inhibitors (AI) for prevention; however, the risk of osteoporotic fractures and complications, such as osteonecrosis of the jaw are substantial with these drugs and may preclude AIs as a viable prevention option in a majority of women.

Although breast cancers are being detected at a much earlier stage and there is considerable work being done with systemically administered agents such as SERMs and AIs to prevent breast cancer, little work with regards to prevention has been done with agents administered locally, either topically on the skin, or instilled directly into the milk ducts via intraductal therapy, as proposed in this study. It is recognized that the majority of breast cancer begins in the lining of the duct. Atypical lesions, such as atypical ductal hyperplasia (ADH) are thought to progress to ductal carcinoma in situ (DCIS) and to invasive

cancer, with a diagnosis of ADH conferring a 30-35% lifetime risk of developing invasive breast cancer. For purposes of preventing breast cancer there is strong rationale to identify these epithelial changes and stop them from ever developing in to carcinoma.

Providing a local therapy into the ducts could reduce the morbidity associated with prevention while targeting the potential carcinoma cell.

This approach is possible because of the anatomy of the breast ductal systems. Cooper did extensive studies in 1845, and noted that there were commonly 7-10 ducts. Subsequently, Sartorius performed mammographic studies, and determined there are 5-9 breast ducts, which coincides with Dietz's findings. A study by Love examined the anatomy of the breast using six complementary *in vivo* and *in vitro* approaches to determine the number, distribution and anatomical properties of the ductal systems of the breast which extend from the nipple orifices to the terminal duct lobular units. Over 90% of the nipples studied contain 5-9 ductal orifices, generally arranged as a central group and a peripheral group. Each nipple orifice communicates with separate non-anastomosing ductal systems which extend to the terminal duct lobular units.

The idea of examining the breast ducts and ductal fluid to understand breast carcinogenesis is not a new concept. The first description by LeBourgne in 1946 was termed "ductal rinse." He inserted a small catheter into the breast duct and instilled saline, removed the catheter and collected the saline as it dripped out of the ductal opening. Subsequently, in 1958, Papanicolaou, also examined breast duct fluid by placing a suction cup on the nipple to elicit small drops of fluid from the breast. He studied the cells that were in the fluid in an attempt to identify abnormalities or cancer, similar to what had been accomplished by the Pap Smear and cervical cytology. Although Papanicolaou was able to identify DCIS in a cellular smear of the nipple aspirate fluid (NAF), there was little to be done with the procedure as there was no therapy available to women other than a mastectomy, which was problematic for those with atypical cells as their significance was still unknown. Because of a lack of appropriate therapy and the advent of mammography, the examination of ductal fluid and nipple ducts fell to the wayside and was not revisited again until the 1970s.

Several researchers in the 1970s began examining ductal fluid by utilizing the suction cup method and analyzing the NAF. Their research revealed that the presence of NAF alone increased the risk of developing breast cancer. Furthermore, that risk became more significant if cellular atypia was identified in the NAF. The risk further increased if the woman had a family history of breast cancer. Additionally, Sartorius, further examined the breast ducts in a similar fashion as LaBourgne, by cannulating the nipple ducts whose NAF contained atypical cells under microscopic examination. After cannulating the ducts, he instilled contrast material, performed a mammogram, then collected the contrast material out of the duct and analyzed it under the microscope. His research demonstrated that the presence of atypical cells in ductal fluid had a significant impact on the risk of developing breast cancer, similar to what had been demonstrated in NAF.

Based upon these compelling results, clinicians began exploring the collection of NAF as well as instilling fluid into the ducts and collecting it, "ductal lavage." One such researcher, Love, developed a small catheter to be used to instill fluid as well as collect fluid

from the breast nipple ducts. The catheter was commercialized through a medical device company, ProDuct Health, Inc. (Menlo Park, CA), which was later acquired by Cytoc, Inc. (Marlborough, MA, USA) in 2001, which in turn was acquired by Hologic (Waltham, MA, USA). Hologic sold the license to the catheters to Atossa Genetics, but unfortunately, it is no longer available.

Initial research shows much promise with regard to intraductal infusion in order to reduce the risk of breast cancer. Researchers have recently demonstrated the feasibility of intraductal delivery of epirubicin. Goulet and colleagues encapsulated epirubicin, a naturally fluorescent anthracycline, into biodegradable nanoparticles. The nanoparticles were then administered into mastectomy specimens in the operating room immediately after a mastectomy was performed, and the tumor specimen was removed for pathologic assessment. They reported that intact epirubicin was seen in the terminal lobules in 8 of 13 specimens. This pilot study demonstrated that it is feasible to use the microcatheter to cannulate the breast ducts and infuse a substance throughout a specific duct, all the way to the terminal lobules.

Based upon numerous preclinical studies in rats and mice, Love reported the feasibility of administering intraductal pegylated liposomal doxorubicin (PLD) or Doxil® into one duct of a woman with a history of breast cancer scheduled for a prophylactic contralateral mastectomy in the unaffected side. The subject reported no discomfort during the procedure and no problems after the procedure. Six weeks subsequent to the procedure, the subject underwent mastectomy histological changes were noted in the lining of the ducts. There was not an opportunity to study the effect of the drug on cancer, as the subject was cancer free. More recently, researchers at Johns Hopkins University determined the intraductal approach to breast cancer and prevention to be of great importance. [name] and her colleagues at Johns Hopkins University reported a clinical study administering Doxil into the breast ducts containing cancer of women prior to mastectomy.

In collaboration with [name], [name] and the Cancer Institute & Hospital at the Chinese Academy of Medical Science conducted a study in 2007 comparing intraductal pegylated doxorubicin, methotrexate and carboplatin in 31 women scheduled to undergo mastectomy. Published results of this study showed that intraductal administration was feasible, but it was suggested that duct perforation led to erratic pharmacokinetics. Study results and conclusion warrant the exploration of additional – possibly less toxic, agents for intraductal therapy.

Building on to these prior studies with cytotoxic agents, this study utilizes the pure anti-estrogen fulvestrant to be injected in up to 5 ducts to determine its effect on the cancer or DCIS as well as the safety of this administration method.

## **5.0 CLINICAL USE OF THE ANTI-ESTROGEN FULVESTRANT (FASLODEX®)**

Fulvestrant is the only endocrine therapy targeting the ER receptor that has been shown to have efficacy in tamoxifen resistant cancers in Phase 3 clinical trials. Two randomized trials have compared the efficacy of fulvestrant 250 mg IM with 1 mg oral anastrozole in postmenopausal women with advanced breast cancer whose disease had progressed after prior endocrine therapy. A combined analysis of these trials showed that fulvestrant was at least as effective as anastrozole (5.5 versus 4.1 months, respectively). Based on these trial

results, fulvestrant gained approval as an intramuscular injection of 250 mg once monthly dose level as a second-line treatment for postmenopausal women with hormone-sensitive breast cancer.

A subsequent randomized trial, CONFIRM, compared 250 mg with 500 mg monthly fulvestrant in 736 women and established a 500 mg dose to be superior in terms of Progression-free survival. At 18 months median follow-up PFS was 6.5 months in the 500 mg arm and 5.4 months in the 250 mg arm ( $p=0.006$ ). This study established 500 mg as the standard dose as described in the product labeling in the US and Europe, with a dose of 250 mg recommended for subjects with moderate hepatic impairment.

Neo-adjuvant use of fulvestrant in postmenopausal women with newly diagnosed invasive breast cancer was evaluated in the randomized “NEWEST” Phase 2 study, which randomized 211 subjects between 500 mg and 250 mg monthly intramuscular fulvestrant (with an extra dose on Day 14 of Month 1) for 16 weeks until surgery. Similar as in the study described in this protocol, change in Ki67 proliferation index 4 weeks after fulvestrant was the primary endpoint. By 4 weeks, the change from baseline in Ki67 labeling index was significantly different between the groups (-78.8 vs. -47.4%,  $p<0.0001$ ). Changes from baseline in ER expression were also significantly different between the groups ( $p<0.0002$ ), but changes in PgR expression were not. No safety concerns were identified.

### **5.1 Intraductal Doses of Cytotoxic versus Endocrine Agents**

Most cytotoxic agents are given based upon BSA, whereas endocrine agents such as fulvestrant or tamoxifen are not.

Consequently, the dose used in this study will not be tailored to BSA or body weight. The maximum dose of 500 mg selected for the study is based on US labeled Intra-Muscular (IM) dose. Since milk ducts differ in size and volume, it may not be possible to administer 500 mg (10 mL) in all subjects.

It is possible, but unlikely, that peak plasma concentrations of a dose given intraductally will reach the same level as the same dose given intramuscularly (IM). This is because the agent must diffuse out of the ducts to reach the bloodstream. Eventually the entire dose will be taken up systemically but it will happen over a longer period of time (the peak plasma concentration will be lower but the area under curve [AUC] should be the same). Hence it was decided that the total amount of drug given in a single intraductal installation would not be higher than the typical IM dose of fulvestrant. There will be 5 groups, each consisting of 6 subjects. The first subject of each group will receive fulvestrant administered intramuscularly and the next 5 subjects will receive fulvestrant intraductally.

A maximum of two 5 mL vials, each containing 250 mg fulvestrant may be delivered into one duct or distributed among up to five ducts targeted for intraductal instillation. Ductal systems range in shape, size and volume just as breasts range in shape and size. As noted before, there are a range of ducts (from 5-9) and each duct within a breast is a different size. The ductal systems have the capacity to accommodate a significant amount of fluid. In a breast feeding woman, a single breast can accommodate anywhere from 47.2 mL to 62.8 mL. In a non-lactating woman, it is estimated that each breast duct can be distended with as little as 1 mL and may accommodate up to 20 mL without perforation and only mild discomfort. Based on prior experience with intraductal therapy it was determined that no

single breast would be administered > 10 mL of fulvestrant, to be divided among up to 5 ducts targeted for instillation. This amount, in a non-lactating subject, would limit the risk of perforation and discomfort associated with intraductal instillation.

### **5.2 Intraductal Effects of Endocrine Agents**

An important strategy in achieving Atossa's goal of developing treatments for the prevention of breast cancer and tissue-sparing alternatives to radical surgery for those with diagnosed breast cancer/DCIS, is to repurpose endocrine agents which are currently available and proven to be effective in treating cancer as a method of prevention. In order to study this, initially, subjects with invasive breast cancer or DCIS will be evaluated.

Atossa plans to evaluate the effect of fulvestrant on the ducts with breast cancer/DCIS as well as ducts without breast cancer in each subject treated in this trial.

### **5.3 Drug Plasma Concentration Levels**

It is estimated that fulvestrant plasma levels at any given time point will be at most the same but more likely less than the levels experienced with IM delivery. It is possible but unlikely that fulvestrant will be concentrated in the plasma at the same level as when given IM but this will be further assessed in this clinical trial.

This clinical trial represents a first step to assess the feasibility and safety of intraductal endocrine therapy with fulvestrant. Hence an understanding of the pharmacokinetic effects of this route of administration is imperative.

## **6.0 TRIAL OBJECTIVES AND PURPOSES**

### **6.1 Primary Objective**

To study the safety and tolerability of intraductal administration of fulvestrant (Faslodex, ICI 182,780) in women with Stage 1 or 2 invasive ductal carcinoma (or mixed ductal and lobular) or DCIS, prior to mastectomy or lumpectomy.

### **6.2 Secondary Objectives**

- a. To determine the pathological effects, specifically changes in Ki67, ER/PgR expression between the pre-fulvestrant biopsy and the post-fulvestrant surgical specimen.
- b. To compare an abbreviated (PK) profile of standard intramuscularly administered (500 mg) with the intraductal instillation of single-dose (500 mg maximum) fulvestrant.
- c. To determine and compare breast tissue fulvestrant distribution.

## **7.0 TRIAL DESIGN**

This is an open-label, non-randomized pharmacokinetic study of pre-surgical fulvestrant in women scheduled for mastectomy or lumpectomy. Eligible subjects will be identified upon admission to the institution for surgical management of breast cancer or DCIS, specifically mastectomy or lumpectomy. There will be 5 groups, each consisting of 6 subjects. The first subject of each group will receive fulvestrant administered intramuscularly and the next 5 subjects will receive fulvestrant intraductally. Subjects where at least 1 suitable duct is identified may undergo nipple aspiration in order to facilitate duct identification and

intraductal infusion of a fulvestrant accompanied by imaging (saline+ ultrasound). A maximum of 5 ducts will receive intraductal infusion of fulvestrant. Across all ducts, the total dose will not exceed 500 mg (10 mL). All subjects will be monitored for systemic and local adverse events during the procedure, immediately following the procedure, within 30 minutes, 1 hour, 4 hours and by phone following discharge on Days +1 and +2, +7, and pre-operative. Subsequent to mastectomy or lumpectomy, subjects will be assessed for systemic adverse events until discharge. Per schedule specified in Table 1, subjects will undergo serial blood draws to determine fulvestrant blood concentration levels.

When fulvestrant is administered at or below the dose level of 500 mg currently in routine clinical use, emergence of Dose Limiting Toxicities (DLT) is unlikely, but not impossible.

Since only a single instillation of fulvestrant is given in this protocol, dose reduction in individual subjects is not possible. However, if any of the DLT parameters reaches any of the thresholds values set in Section 10.3 the dose in subsequent subjects will be reduced to 250 mg (one 5 mL vial).

The purpose of this observational study is to understand the safety and tolerability of giving the anti-estrogen drug fulvestrant directly into the milk ducts of the breast, and collect any evidence of pathologic response. This study will be conducted under good clinical practice (GCP) guidelines as outlined in Section 15.5 Good Clinical Practice. This will be a single-dose study with two treatment groups: 500 mg administered intramuscularly (n=6) and up to 500 mg administered intraductally (n=24).

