## 9.0 TREATMENT OF SUBJECTS

### 9.1 Study Related Procedures

After each subject has reviewed and signed the informed consent, she will be enrolled in the study and assigned a study number as outlined below in Section 17.3 Data Collection Requirements. Further testing maybe necessary to determine eligibility and will commence upon enrollment. These tests are included in Section 9.2 Baseline Assessment. Some of the exams, tests or procedures may be a part of routine care for breast cancer and may be used as baseline assessments if conducted no more than 2 weeks prior to participation in the study. Other tests are only being done for the purpose of the study. A member of the study staff will go over, in detail, with each subject the tests that are being done specifically for the study and those that are considered routine care.

All subjects will receive fulvestrant, but the actual total dose received may vary within subjects receiving fulvestrant intraductally, as it is guided by the number of accessible ducts and volume of the ducts.

The first subject of each group will receive intramuscular (IM) fulvestrant (500 mg) and the next five subjects of that group will receive intraductal (ID) fulvestrant up to 500 mg. There are five groups, for a total of 30 subjects. After fulvestrant instillation, both signs and symptoms of local (breast and chest wall) and systemic toxicity will be evaluated using the CTCAE v. 5.0. Each Group – IM; ID, ID, ID, ID, ID.

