### **13.2 Sample Size and Statistical Analyses**

A total of 30 subjects who are undergoing mastectomy or lumpectomy will be included in this study: 6 will receive intramuscular, and 24 will receive intraductal fulvestrant. With respect to the sample size for the latter group with 24 subjects, it will be possible to detect an effect size of approximately 0.60 with 80% power and 0.69 with 90% power. Both of these are in the medium to large range according to Cohen's terminology and are based on the demonstration of a reduction in the Ki67 labeling index mean from baseline (diagnostic biopsy) to week 4 (surgically excised specimen) using a paired t-test. With these effect sizes and an anticipated 50% decline in the mean index, then the expectation would be a standard deviation in this reduction of about  $\pm 83.7\%$  for 80% power and  $\pm 72.3\%$  for 90% power.

The primary endpoint of this study is to assess safety and tolerability as measured by adverse events, subject pain assessment as well as signs of topical irritation seen on the excised specimen. In addition, the effect of the administration will be evaluated with respect to the change in Ki67 labeling index (primary efficacy endpoint) and changes in estrogen and progesterone receptor expression (secondary efficacy endpoints)

Descriptive statistics will be used to summarize the data (means/medians and standard deviations/interquartile ranges for quantitative data and proportions/percentages for categorical data such as adverse events), and numerically compare the groups with entry diagnoses of invasive ductal carcinoma and DCIS, respectively. In addition, the 6 study subjects who receive intramuscular fulvestrant will be qualitatively compared with the main study cohort of 24 subjects who receive intraductal fulvestrant.

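### The allocation rule gives 5 IM and 25 ID subjects, not the stated 6 and 24; the printed order also makes every route known in advance and should be concealed when the text is corrected

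*Combined protocol and SAP*

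**What the plan says.** Section 7.0 describes the trial thus: "This is an open-label, non-randomized pharmacokinetic study of pre-surgical fulvestrant in women scheduled for mastectomy or lumpectomy". The synopsis gives one site.

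The allocation rule is in 7.0: "There will be 5 groups, each consisting of 6 subjects", and "The first subject of each group will receive fulvestrant administered intramuscularly and the next 5 subjects will receive fulvestrant intraductally". Section 5.1 repeats it, 9.3.1 and 9.3.2 apply it, and 9.1 prints the sequence as "Each Group – IM; ID, ID, ID, ID, ID".

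The arm sizes are stated differently. Section 13.2 says "6 will receive intramuscular, and 24 will receive intraductal fulvestrant", and the synopsis and the last paragraph of 7.0 give the same 6 and 24. The detectable effect sizes in 13.2 are for the 24 ID subjects.

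The two routes are compared in three places:

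- Secondary objective (b) in 6.2: "To compare an abbreviated (PK) profile of standard intramuscularly administered (500 mg) with the intraductal instillation of single-dose (500 mg maximum) fulvestrant".
- Secondary objective (c), on the distribution of drug in breast tissue.
- A qualitative contrast of the IM and ID subjects in 13.2.

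Under 8.3 the study number follows confirmation of eligibility, whereas 9.1 gives it at enrolment, before any further eligibility testing. Section 8.4 replaces subjects who withdraw before surgery but does not say which route the replacement receives. No section describes concealment, central assignment or a consecutive-enrolment rule.

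**The concern.** There are two matters, of different weight.

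First, the rule that staff will follow and the arm sizes on which the statistics section rests do not agree. A site that follows 7.0 to the letter will finish with one IM subject fewer and one ID subject more than 13.2 expects. The IM arm is the smaller one and, in the synopsis, the reference for Ki67 response and PK.

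Second, anyone at the site can read off the route of the next subject. Which woman is approached next, and when, can therefore depend on the route waiting for her. Section 7.0 ties the ID procedure to finding at least one suitable duct, but no inclusion criterion in 8.1.1 requires one, and 9.1 says that the ID dose delivered depends on how many ducts are accessible and on their volume. Enrolment that favoured women with accessible ducts for ID slots would thus bear on the ID exposure that objective (b) compares. With 5 or 6 IM subjects, adjustment in the analysis is not realistic; the only covariates that 13.3 mentions are body-size terms in the joint PK fit.

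**Working it through.** **1. The plan's own power figure.** Inputs from 13.2: n = 24, paired t-test, 50% mean decline. Alpha and sidedness are not stated; two-sided 0.05 is assumed. With 23 degrees of freedom and noncentrality d√24:

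- 80% power: d = 0.597, implied SD = 50/0.5972 = 83.7%.
- 90% power: d = 0.691, implied SD = 50/0.6911 = 72.3%.

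Both match the plan (0.60 and 0.69; 83.7% and 72.3%). One-sided 0.05 gives 0.523 and 0.616 and does not match. The figure was therefore worked out for 24 ID subjects.

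**2. Arm sizes under the rule.**

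- IM: 5 groups × 1 = 5.
- ID: 5 groups × 5 = 25.
- Stated: 6 and 24. Total in both cases: 30.

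One structure that would give the stated split is six blocks of five: 6 × (1 + 4) = 6 IM and 24 ID.

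**3. What 25 instead of 24 does to power.** The same calculation with n = 25 gives d = 0.584 (80%) and 0.676 (90%), with SDs of 50/0.584 = 85.6% and 50/0.6759 = 74.0%. Power at d = 0.60 moves from 80.4% to 82.1%, and at d = 0.69 from 89.9% to 91.1%.

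**4. Predictability.** As written, all 30 of 30 routes are known in advance. For a random list whose composition is known and whose past assignments are visible, an assignment is certain once one route is used up. The expected number of certain assignments is

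(number of ID)/(number of IM + 1) + (number of IM)/(number of ID + 1).

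- Blocks of five (1 IM, 4 ID), size known: 4/2 + 1/5 = 2.2 of 5, or 44%.
- One list of 30 (6 IM, 24 ID): 24/7 + 6/25 = 3.43 + 0.24 = 3.67 of 30, or 12%.
- One list of 30 (5 IM, 25 ID): 25/6 + 5/26 = 4.17 + 0.19 = 4.36 of 30, or 15%.

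**5. Possible size of a selection effect.** If m of n IM subjects differ by b SD from those they displace, the IM mean shifts by m × b/n. The documents give neither m nor b. Over the assumed range m = 1 to 3 and b = 0.5 to 1.0:

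| IM subjects | smallest (m = 1, b = 0.5) | m = 1, b = 1 | m = 2, b = 1 | largest (m = 3, b = 1) |
|---|---|---|---|---|
| 6 | 0.08 SD | 0.17 SD | 0.33 SD | 0.50 SD |
| 5 | 0.10 SD | 0.20 SD | 0.40 SD | 0.60 SD |

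**6. Comparison with chance error.** The standard error of IM minus ID, in SD units, is √(1/6 + 1/24) = 0.456 at 6/24 and √(1/5 + 1/25) = 0.490 at 5/25. With 28 degrees of freedom the 95% half-widths are about 0.93 SD and 1.00 SD.

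**The case against.** The design is openly declared non-randomized, the primary objective is the safety of the ID route, and no between-arm test is planned. The Ki67 analysis compares each subject with herself, so the order of allocation does not enter it. A reader might infer that the printed order biases the Ki67 result; 13.2 does not support that, because its IM/ID contrast is only qualitative and does not name Ki67.

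The means of steering are limited. Moving a subject into another slot would breach 9.3.1 and 9.3.2 and count as a departure to be documented under 15.6, so what remains is the timing of enrolment. Section 9.3.4 applies one 14 to 45 day window before surgery to both routes and says that taking part does not alter the surgery date; nothing shows why an early date would favour IM. Nor is it clear why ducts that are hard to cannulate would make plasma levels after an intramuscular injection atypical. The ID arm could lose difficult cases, but each is only 1/24 of its mean.

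Any shift of the sizes above also sits inside the chance error of so small a comparison.

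Most of this stands. It confines the allocation matter to objectives (b) and (c) and the descriptive contrast, and makes it an improvement rather than an error. It does not answer the arm count, which is exact. Nor does chance error excuse selection altogether: a selection effect is systematic, and no confidence interval reflects it.

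**Conclusion.** The contradiction in arm sizes is certain and rests on no assumption: 5/25 under the rule, 6/24 in the synopsis, 7.0 and 13.2. The documents do not settle which is intended. Its effect on power is slight, about 1 to 2 percentage points under two-sided 0.05, but the allocation text and the statistics section cannot both be followed.

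The known order is an unprotected risk of selection in the IM/ID comparisons. Its possible size, 0.08 to 0.60 SD in the IM mean over both arm sizes, depends wholly on assumed values and is below the 95% half-width of 0.93 to 1.00 SD. Three stronger readings should be resisted:

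- That subjects are being steered. The documents show only that it is possible.
- That the miscount is evidence of selection. It is a separate defect in the same text.
- That a concealed random list would remove the problem. In an open-label trial with known blocks of five, 44% of assignments would still be certain beforehand.

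**What to change.** **Required.** Choose the arm sizes and use them in the synopsis, 5.1, 7.0, 9.1, 9.3.1, 9.3.2 and 13.2. Either write an allocation that delivers 6 IM and 24 ID, or restate the arms as 5 and 25 and base 13.2 on n = 25 (0.58 and 0.68, with SDs of about 85.6% and 74.0%).

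**Advised in the same amendment.**

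- Replace the fixed order with a concealed random list that delivers the chosen sizes, for example 6 IM placed at random among 30, or blocks whose size is not disclosed to the site.
- Open each assignment only after eligibility is confirmed, as 8.3 allows, and bring 9.1 into line with 8.3.
- State in 8.4 that a replacement takes the route of the subject replaced. This holds the arm sizes, although that one route is then known.
- Keep the IM/ID comparison descriptive.

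**Cost.** No added subjects or study procedures. A signed amendment (15.2) with IRB approval (15.6) is needed, possibly with revised consent and re-consent. ID procedures can be scheduled only once the assignment is opened.
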